### **10.3. Concomitant treatments**

Concomitant treatments are coded using the WHO-DRUG dictionary version 2022 Q1.

All treatments taken at least once after reference first date or appeared during the study will be summarised by Anatomical Therapeutic Class (ATC) and substance name. The number and percentage of subjects in each category will be computed.

Subjects will be counted only once within these ATC categories. They will be analysed on the FAS.

Note: a medication which began before the reference start date and which is ongoing after the reference start date is counted in “previous medications” (see §8.2) and not in “concomitant medications”.

#### 10.4. Non-related adverse events

In the following paragraph, for a smoother reading:

- adverse events will be referred as AE;
- treatment-emergent adverse events will be referred as TEAE.

Adverse events are coded using the MedDRA dictionary version 25.0. They are classified by System Organ Class and Preferred Term.

For efficacy analyses, only non-related AEs are considered, i.e. adverse events with a relationship to study device equal to “not related”. These analyses will be performed on the Safety Set.

An adverse event will be considered as a treatment-emergent adverse event (TEAE) if:

- it was reported at least one day after screening;
- it was not present prior to the reference start date;
- it was present prior to the reference start date and worsened during the study (increase of intensity);
- it reappears after the reference start date (finished before the reference start date).

Missing or incomplete dates will be estimated as described in §6.4.4 in order to determine the TEAEs, but they will be presented as reported in CRF in the data listings. Generally, an adverse event for which the onset date is missing or incomplete and does not permit to identify the onset according to the date of the reference start date (i.e. missing onset day and month/year corresponding to the reference start date) will be considered as treatment-emergent.

Note: if the intensity/severity is missing, a conservative approach will be adopted and the intensity/severity will be considered as severe.

A given treatment-emergent adverse event (according to the MedDRA terminology) will be counted only once per subject. If a subject experienced several AEs in the same SOC/PT, the most severe intensity will be retained for this SOC/PT.

- Summary of non-related adverse events

A summary table will be produced:

- number and percentage of subjects with at least one non-related adverse event (AE);
- number and percentage of subjects with at least one non-related AE leading to definitive study device discontinuation;
- number and percentage of subjects with at least one non-related AE leading to definitive study discontinuation;
- number and percentage of subjects with at least one non-related TEAE.

The number of non-related AEs of each category will also be provided in this table.

- Analysis of non-related treatment-emergent adverse event

---

The number and percentage of subjects with non-related TEAEs will be summarised by System Organ Class and Preferred term.

The number of non-related TEAEs of each category will also be provided in this table.

All non-related AEs leading to definitive discontinuation of the trial device or to definitive discontinuation of the study will be listed if applicable.

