### **5.2 Anticipated adverse device effects**

The only expected adverse event is the feeling of itching and irritation while initiating the treatment with the investigational medical device **Healsea® Rescue\***. In case of such adverse reaction, the patients will be instructed to report the incident into the e-diary and to contact the investigator if the patient wishes to stop the nasal spray use.

No adverse effect is expected with **the Placebo**.

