#### **Expected and foreseeable side effects (MEDDEV 2 12-1 rev. 8)**

They meet all the following criteria:

- Clearly identified in the manufacturer's labelling,
- Clinically well known as being foreseeable and having a certain qualitative and quantitative predictability when the device is used and performs as intended,
- Documented in the device master record, with an appropriate risk assessment, prior to the occurrence of the incident and,
- Clinically acceptable in terms of the individual patient benefit.

**Adverse event** means any untoward medical occurrence, unintended disease or injury or any untoward clinical signs, including an abnormal laboratory finding, in subjects, users or other persons, in the context of a clinical investigation, whether related or not related to the investigational device (MDR 2017/745).

Adverse or intercurrent events are graded as follows:

- Mild: Awareness of signs or symptoms but easily tolerated.
- Moderate: Uncomfortable enough to cause interference with usual activity.
- Severe: Incapacity with inability to work or do usual activity.

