### 11.2. Incidents and expected side effects

For safety analyses, only incidents and expected side effects are considered, i.e. adverse events with a relationship to study device other than “not related”.

- Summary of incidents

A summary table will be produced:

- number and percentage of subjects with at least one incident;
- number and percentage of subjects with at least one incident leading to definitive study device discontinuation;
- number and percentage of subjects with at least one incident leading to definitive study discontinuation;
- number and percentage of subjects with at least one serious incident.

The number of incidents of each category will also be provided in this table.

- Analysis of incident

The number and percentage of subjects with incidents will be summarised by System Organ Class (SOC) and Preferred term (PT).

The number of incidents of each category will also be provided in this table.

A listing of serious incidents will be provided if applicable.

All incidents leading to definitive discontinuation of the trial device or to definitive discontinuation of the study will be listed if applicable.

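### No planned summary table shows event intensity, and the intensity rules in SAP 10.4 do not reach the device-related events in SAP 11.2, so the severity of non-serious local reactions is not summarised by arm

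*SAP*

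**What the plan says.** **Grading.** Protocol 14.2 introduces a three-level scale with the words "Adverse or intercurrent events are graded as follows". The levels run from easily tolerated, through interference with usual activity, to incapacity.

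**Rules for intensity.** SAP 10.4, which covers only events judged unrelated to the device, has two: "if the intensity/severity is missing, a conservative approach will be adopted and the intensity/severity will be considered as severe", and "If a subject experienced several AEs in the same SOC/PT, the most severe intensity will be retained for this SOC/PT". The same section also counts a pre-existing event as treatment-emergent if its intensity increased during the study.

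**Outputs for unrelated events.** SAP 10.4: "The number and percentage of subjects with non-related TEAEs will be summarised by System Organ Class and Preferred term". Event counts are added.

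**Outputs for related events.** SAP 11.2 opens with "For safety analyses, only incidents and expected side effects are considered", meaning events with any relationship to the device other than unrelated. It then states: "The number and percentage of subjects with incidents will be summarised by System Organ Class (SOC) and Preferred term (PT". A second table counts incidents overall, serious incidents, and incidents that ended device use or participation. Neither intensity rule is repeated.

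**The expected harm and the objective.** Protocol 5.2: "The only expected adverse event is the feeling of itching and irritation while initiating the treatment with the investigational medical device". The same section expects no adverse effect from placebo. SAP 2.2 lists systemic and local tolerance as the safety objective.

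**The concern.** Keeping the worst grade per patient and term serves a purpose only if some output displays the grade, and no summary table does. The rules are also missing from the section where they would matter most: itching and irritation judged related to the spray falls under 11.2, not 10.4.

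What is at stake is how informative the local-tolerance result will be. A count of patients with irritation cannot separate a sensation that is easily tolerated from one that interferes with usual activity, although the protocol's own scale makes that distinction and the grade is collected.

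**Working it through.** This is mainly a document check; the plan gives no figure on this point to reproduce.

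**Step 1. Look for intensity in each planned summary table** (SAP 13.1 list, 13.2 mock tables).

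| Table | Content | Intensity shown? |
|---|---|---|
| 14.2.4.1.1, summary of unrelated events | n (%), event count; any event, two discontinuation rows, TEAE | No |
| 14.2.4.1.2, unrelated TEAEs by SOC/PT | n (%), event count | No |
| 14.3.1.1 in the list, 14.3.1.3 in the mock: summary of incidents | n (%), event count; any, two discontinuation rows, serious | No |
| 14.3.1.2 in the list, 14.3.1.4 in the mock: SOC/PT table for related events | n (%), event count | No |

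Result: 0 of 4.

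**Step 2. Ask whether the worst-intensity rule changes any number.** In a SOC/PT table, n counts patients with at least one event. It is the same whichever of a patient's intensities is retained. The event count is also unaffected. The rule has no visible use in these tables.

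**Step 3. Find where intensity is used.**
- In SAP 10.4, to decide whether a pre-existing event worsened. Setting a missing grade to severe can affect that classification.
- As a column in mock Listings 14.2.4.2.X and 14.3.2.X. These cover events leading to discontinuation and, for incidents, serious ones.
- Possibly in Listing 16.2.7.1, which covers all events; its columns are not shown.

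**Step 4. See whether the satisfaction endpoint fills the gap.** SAP 10.2.4 names local tolerance, but the questions in mock Table 14.2.2.4 are about ease of use, residual taste, cleansing and moistening, and recommendation. None asks about irritation.

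**Step 5. Illustrate the size.** The 100 patients per arm come from SAP 4. Everything else is assumed: equal irritation incidence, one event per affected patient, all non-serious, all continuing treatment, and a moderate or severe share of 50% in one arm and 10% in the other. Cases = 100 × incidence × share.

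| Incidence, both arms | Planned SOC/PT row | Moderate or severe | Fisher, two-sided p |
|---|---|---|---|
| 10% | 10 vs 10 | 10 × 0.5 = 5 vs 10 × 0.1 = 1 | 0.21 |
| 20% | 20 vs 20 | 10 vs 2 | 0.033 |
| 30% | 30 vs 30 | 15 vs 3 | 0.005 |

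In every line the planned row is identical between arms (p = 1.00). The p-values only give a sense of scale; no such test is planned or proposed.

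**The case against.** The strongest reply is that nothing promised is missing. Protocol 8.4 commits to numbers and percentages by SOC and PT, not to a tabulation by intensity, and the SAP delivers that. The grade is collected, so a table could be produced later. This stands, and it is why the point is a reporting improvement and not an error.

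Second, severe reactions would not necessarily be hidden. Protocol 5.2 foresees that a patient with irritation may wish to stop the spray, and device discontinuations due to incidents are tabulated by arm. This also stands. Suppose 10 irritation cases per arm with 5 against 0 severe: the one-sided Fisher p is C(100,5)/C(200,5) = 75,287,520/2,535,650,040 = 0.030, and the two-sided p is 0.059. The incident tables would be the same in both arms only if none of those five stopped treatment or had a serious incident. What remains uncovered is the non-serious reaction in a patient who continues, for whom discontinuation rows give no information.

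Third, a reader might infer more than the documents support:
- *That the trial could declare tolerance similar when it is not.* No comparative safety conclusion is planned. The objective is to assess tolerance of the device, SAP 6.3.1 makes everything beyond the primary criterion descriptive, and no between-arm safety test is specified.
- *That intensity is never used.* It enters the treatment-emergent classification and some listings.
- *That the worst-intensity rule already governs irritation judged related to the device.* It is written for unrelated events only.
- *That irritation is expected to be mild.* The documents describe a feeling of itching and irritation when treatment starts and give no usual grade.

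**Conclusion.** The point holds as a minor one. The worst-intensity rule has no visible use, SAP 11.2 has no intensity rule, and the severity of non-serious local reactions in patients who continue treatment is not summarised by arm despite the local-tolerance objective.

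The size in this trial cannot be stated, because the documents give no irritation rates. The counts above rest on assumed incidence and assumed grade shares, and at 10% incidence even a fivefold difference (5 vs 1) is within chance. The conclusion does not depend on them: it rests on the content of the four tables. It assumes that the mock tables show the intended columns. If Listing 16.2.7.1 carries intensity, the information will be available patient by patient, but still not summarised by arm. The primary efficacy analysis and its error rate are not affected.

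**What to change.** 1. Move the two intensity rules (missing set to severe; worst grade per patient and SOC/PT) to a general paragraph that covers both SAP 10.4 and 11.2.
2. Add maximum intensity (mild, moderate, severe) by arm to the SOC/PT table for incidents and to Table 14.2.4.1.2, counting each patient once per PT at the worst grade.
3. Show in each table how many intensities were imputed as severe, so that missing grades cannot pass for observed severe reactions.
4. Reconcile the incident tables. The SOC/PT table is 14.3.1.2, titled as related TEAEs, in the SAP 13.1 list, but 14.3.1.4, titled as incidents, in the mock. The incident summary is 14.3.1.1 in the list and 14.3.1.3 in the mock.
5. State that Listing 16.2.7.1 includes intensity.

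The output stays descriptive and needs no between-arm test. The cost is two wider tables and a few lines of SAP text. No new data are needed and no study procedure changes.

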## 11. SAFETY

The following analyses will be performed on the Safety Set.

### 11.1. Study duration

Study duration will be calculated according to the formula below:

$$\text{Study duration (days)} = \text{Reference End Date} - \text{Reference Start Date} + 1$$

It will be described (see §6.2) on the Safety Set.

### 11.2. Incidents and expected side effects

For safety analyses, only incidents and expected side effects are considered, i.e. adverse events with a relationship to study device other than “not related”.

- Summary of incidents

A summary table will be produced:

- number and percentage of subjects with at least one incident;
- number and percentage of subjects with at least one incident leading to definitive study device discontinuation;
- number and percentage of subjects with at least one incident leading to definitive study discontinuation;
- number and percentage of subjects with at least one serious incident.

The number of incidents of each category will also be provided in this table.

- Analysis of incident

The number and percentage of subjects with incidents will be summarised by System Organ Class (SOC) and Preferred term (PT).

The number of incidents of each category will also be provided in this table.

A listing of serious incidents will be provided if applicable.

All incidents leading to definitive discontinuation of the trial device or to definitive discontinuation of the study will be listed if applicable.

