**-Safety:**

All adverse events/incidents/expected side effects will be listed, but only treatment-emergent adverse events/incidents (non-serious + serious) will be summarized.

Adverse events/incidents/expected side effects will be summarized by the number and percentage of patients (by treatment group), classified by System Organ Class and Preferred Term as defined by MedDRA dictionary.

For a given treatment group, a given adverse event will be counted treatment emergent only once per patient during the treatment period.

Frequency and percentage of patients with at least one reported adverse event/ incident / expected side effects will be tabulated by System Organ Class and by treatment group.

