**SAFETY – INCIDENTS**

Table	14.3.1.1	Summary of incidents – Safety Set
Table	14.3.1.2	Related treatment-emergent adverse events by System Organ Class and Preferred Term – Safety Set
Listing	14.3.2.1	Listing of serious incidents – Safety Set (if applicable)
Listing	14.3.2.2	Listing of incidents leading to definitive discontinuation of the trial device – Safety Set (if applicable)
Listing	14.3.2.3	Listing of incidents leading to definitive discontinuation of the study – Safety Set (if applicable)

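### SAP safety tables cover device-related events only, so no summary shows the seriousness of unrelated events or the number of patients per arm with any TEAE or any serious event

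*SAP*

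**What the plan says.** **Protocol.** Section 8.4, under Safety, says that all events will be listed but "only treatment-emergent adverse events/incidents (non-serious + serious) will be summarized". It adds that patients with at least one adverse event, incident or expected side effect will be tabulated by System Organ Class and group. The synopsis has the same plan. Neither sentence is limited by causality. Protocol 14.2 defines an adverse event irrespective of its relationship to the device, and the safety objective is systemic and local tolerance.

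**SAP, device-related events.** Section 11.2 opens: "For safety analyses, only incidents and expected side effects are considered", and explains these as events with any relationship to the device other than not related. Its summary includes the "number and percentage of subjects with at least one serious incident", and it provides a listing of serious incidents (14.3.2.1).

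**SAP, unrelated events.** Section 10.4 sits in the Efficacy chapter and says: "For efficacy analyses, only non-related AEs are considered". Its summary has four rows: any unrelated AE, two kinds of discontinuation, and the "number and percentage of subjects with at least one non-related TEAE". Mock Table 14.2.4.1.1 has the same four rows. The only listings attached to 10.4 are of unrelated AEs that led to stopping the device or the study.

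**SAP, elsewhere.** The table list in 13.1 has no table that pools the two classes. The one output covering all events is subject listing 16.2.7.1. Section 12, on changes to the planned analysis, discusses only symptom duration.

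**The concern.** A reader of the report will want to know how many patients in each arm had any treatment-emergent event and how many had any serious event. These are the standard all-cause comparisons. They are also the ones that do not rest on an investigator's causality judgement for each event. Protocol 8.4 leads the reader to expect them.

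Under the SAP, the safety chapter answers only for events judged related. The other events are summarised in another chapter, and there the serious ones are not separated from the rest. A complication of the cold that put a patient in hospital and was judged unrelated would be counted alongside trivial events.

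The split is also by relationship to the device alone. Protocol 5.3 plans two nasopharyngeal swabs, and Protocol 14.4.2 makes serious events related to a study procedure reportable. A serious event caused by a swab but not by the device would fall into SAP 10.4, where no summary marks it as serious.

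**Working it through.** The documents give no figure to reproduce, so the check sets the planned outputs side by side and then asks what can be derived from them.

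**Step 1. What each set of outputs shows, by arm**

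| Quantity | Related (SAP 11.2) | Unrelated (SAP 10.4) | Either |
|---|---|---|---|
| Any event, patients and events | Yes | Yes | No table |
| Treatment-emergent | Unclear (step 3) | Yes | No table |
| Serious | Yes | No | No table |
| Led to discontinuation | Yes | Yes | No table |
| By SOC/PT | Yes | Yes, treatment-emergent only | No table |
| Listing of serious events | 14.3.2.1 | None dedicated | 16.2.7.1, all events |

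**Step 2. Follow one unrelated serious event.** It adds one to the any-AE row of Table 14.2.4.1.1. If treatment-emergent, it is also counted in that table's TEAE row and in the SOC/PT Table 14.2.4.1.2. No row in either table marks it as serious. If it led to discontinuation, it is in listing 14.2.4.2.1 or 14.2.4.2.2, whose mock layout has a column for seriousness. Otherwise it is identifiable only in listing 16.2.7.1. The SAP gives no mock layout for that listing, so a seriousness column there is an assumption.

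**Step 3. Event totals.** The two classes are exclusive and exhaustive for each event, and both summaries report events as well as patients. So for each arm:

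all events = unrelated events + related events.

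This takes the incident rows to include expected side effects, as the opening of 11.2 implies. For treatment-emergent events the sum is less secure. The table list titles 14.3.1.2 as related treatment-emergent events, while the text of 11.2 and the corresponding mock table (numbered 14.3.1.4) report incidents with no such restriction.

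**Step 4. Patients with any event.** One patient can have both a related and an unrelated event. With *a* patients having an unrelated event, *b* a related one, and *n* in the arm:

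max(a, b) ≤ patients with any event ≤ min(a + b, n).

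Assumed counts, for illustration only, with n = 100 as the planned number per arm:

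- a = 15, b = 10: max(15, 10) = 15 to 15 + 10 = 25.
- a = 20, b = 10: 20 to 20 + 10 = 30.
- a = 30, b = 20: 30 to 30 + 20 = 50.

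The same bounds hold for treatment-emergent events if both tables are on that basis.

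**Step 5. Patients with any serious event.** Let *s* be the patients with a serious incident, which is tabulated. The number with an unrelated serious event is not tabulated. From the tables alone it can be anything from 0 to *a*. So:

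s ≤ patients with any serious event ≤ min(s + a, n).

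With the assumed a = 15, the tables leave a range up to 15 patients wide. The discontinuation listings could narrow it, but only for events that led to stopping.

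**The case against.** The strongest reply is that nothing is lost. Both classes are tabulated by arm on the Safety Set, every event is listed, and investigators are blinded (Protocol 7.1.2), so causality is judged without knowledge of the arm. The slashes in Protocol 8.4 can be read as asking for each class to be summarised, not for one pooled table. The split follows the protocol's own post-market framework, which defines and handles incidents and adverse events separately. Non-primary results are descriptive (SAP 6.3.1). Serious unrelated events should also be rare: Protocol 4 puts bacterial sinusitis requiring antibiotics at 0.5 to 2.0%, which for 200 patients is 200 × 0.005 = 1 to 200 × 0.02 = 4, and not all of those would be serious.

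Much of this stands. A reader might infer that unrelated serious events appear in no table, or that none of them is shown. The documents do not support that: these events are counted as ordinary AEs in Table 14.2.4.1.1 and, if treatment-emergent, in 14.2.4.1.2, and they are listed in 16.2.7.1. Nor is it right that nothing can be added across the two classes, since overall event totals can. Placing 10.4 under Efficacy is odd but changes no number.

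The reply does not reach the patient counts or the missing serious row. Even on the looser reading of the slashes, Protocol 8.4 has serious and non-serious treatment-emergent adverse events summarised, and the unrelated-AE summary does not distinguish them. Small expected numbers make the gap modest, but a handful of serious events is exactly what a report should show by arm.

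**Conclusion.** The point holds as a reporting gap that should be closed. As planned, no summary table shows the seriousness of an unrelated event, and the number of patients per arm with any TEAE, or with any serious event, cannot be derived from the tables. This departs from the plainest reading of Protocol 8.4, and SAP 12 does not record it.

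The size depends on how many patients fall in both classes and how many unrelated events are serious, and the documents give neither. The illustrative ranges, such as 15 to 25 patients per 100, rest on assumed counts and are not a forecast. The primary endpoint, its test and the power are untouched. The documents give no reason to think that events would be concealed or that blinded causality judgements would favour one arm.

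**What to change.** 1. Add to SAP section 11, on the Safety Set, one table by arm regardless of relationship. Give patients and events for any TEAE, any serious AE, and AE leading to device or study discontinuation, with a breakdown by SOC/PT.
2. Add a serious row to Table 14.2.4.1.1.
3. Add a listing of all serious events regardless of relationship to the device.
4. Keep the related/unrelated split as a sub-display, and settle whether Table 14.3.1.2 is restricted to treatment-emergent events, so that its title, the text of 11.2 and the mock table agree.
5. Record the change from Protocol 8.4 in SAP section 12.

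Moving 10.4 to the Safety chapter is sensible but optional.

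The cost is one table, one row, one listing and some SAP wording. All of it uses data already collected, and no other analysis changes.

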##### **Blinding and unblinding:**

The randomization list will be drawn up by Axiodis using a validated software and before the beginning of the study, by a statistician not involved in the study. The master randomization list will be stored confidentially until the study blind is broken at the end of study.

The randomization list will be:

- Transmitted by Axiodis to the responsible of the product preparation, Creapharm
- Uploaded into the patient enrolment module of the eCRF

In case of dysfunction of the Medical Device, it will be possible to attribute a new randomisation number to the patient and a new identical treatment (in a blinded manner) using the eCRF back-up randomisation module.

During the whole study and in the absence of unblinding, neither the investigators nor the subjects nor the staff involved (CRO, sponsor...) will be aware whether the product is Healsea® Rescue\* or the Placebo. Every effort will be made to maintain the blind during the study as well as during the follow-up period.

Both Medical Device (Healsea® Rescue\* and Placebo) will be indistinguishable: same aspect, same packaging and same labelling of the vials.

The unblinding will occur after the database locking, at the end of the study. The person responsible for the randomization list will be in charge of the unblinding.

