**Strictly Confidential**

possible malfunction before the patient leaves the site. In case of dysfunction, a new randomisation number and a new treatment will be attributed to the patient using the eCRF back-up randomisation module.

*NB: The first use of the device will be performed in the evening of the Day 1.*

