### **14.2 Definitions**

**Incident** means any malfunction or deterioration in the characteristics or performance of a device made available on the market, including use-error due to ergonomic features, as well as any inadequacy in the information supplied by the manufacturer and any undesirable side-effect (MDR 2017/745).

**Serious incident** means any incident that directly or indirectly led, might have led or might lead to any of the following: (a) the death of a patient, user or other person, (b) the temporary or permanent

serious deterioration of a patient's, user's or other person's state of health, (c) a serious public health threat (MDR 2017/745).

**Serious public health threat** means an event which could result in imminent risk of death, serious deterioration in a person's state of health, or serious illness, that may require prompt remedial action, and that may cause significant morbidity or mortality in humans, or that is unusual or unexpected for the given place and time (MDR 2017/745).

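### SAP 11.2 equates incidents with device-related adverse events, so malfunctions, use errors and information inadequacies without a medical event, which Protocol 14.2 counts, fall outside the incident tables

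*SAP*

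**What the plan says.** **SAP 11.2** limits the safety analyses to incidents and expected side effects, and explains these, by an i.e., as "adverse events with a relationship to study device other than" *not related*. The incident summary, the breakdown by System Organ Class and Preferred Term, and the listings of serious incidents and of incidents leading to discontinuation all follow from that sentence.

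**Protocol 14.2** says that an incident "means any malfunction or deterioration in the characteristics or performance of a device made available on the market". It includes use error due to ergonomic features, inadequate manufacturer information and undesirable side effects. A serious incident is "any incident that directly or indirectly led, might have led or might lead to any of the following", the list being death, serious deterioration in health and serious public health threat. An adverse event is defined separately, as "any untoward medical occurrence, unintended disease or injury or any untoward clinical signs, including an abnormal laboratory finding".

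**Protocol 7.1.2 and 7.4.1** foresee device failure. The investigator primes the pump at Visit 1 to detect a malfunction, and "In case of dysfunction, a new randomisation number and a new treatment will be attributed to the patient".

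**Protocol 14.3** requires all incidents, and risks of incident, to be entered in the e-CRF. **Protocol 8.4** names incidents next to adverse events among the things to be summarised.

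**The concern.** The two documents use one word for two different sets of events. The protocol's incident is a device concept and needs no medical consequence. The SAP's incident is a subset of adverse events, which by the protocol's definition do need one. A pump that fails in use without causing symptoms is an incident under the protocol but has no place in the SAP's definition.

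What is at stake is the meaning of one labelled result. SAP section 3 describes a post-market clinical follow-up study, and Table 14.3.1.1 will carry a row for subjects with at least one incident. A reader who knows the protocol definition would take a zero in that row to mean that no device failed. Under the SAP rule it would mean only that no device-related adverse event was recorded. The row for serious incidents has the same defect, because an event that might have caused serious harm but did not is excluded.

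**Working it through.** The plan gives no malfunction rate or expected incident count, so there is no figure to reproduce. The check is a comparison of definitions.

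**Step 1. Which events meet each definition?**

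| Event | Incident under Protocol 14.2 | Incident under SAP 11.2 |
|---|---|---|
| Undesirable side effect rated as related to the device | Yes | Yes |
| Malfunction or use error that causes a related adverse event | Yes | Yes, through the adverse event |
| Malfunction or use error with no medical event | Yes | No |
| Inadequate manufacturer information with no medical event | Yes | No |
| Incident that might have led to serious harm, no adverse event | Yes, serious | No |

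The loss is confined to the last three rows.

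**Step 2. Does another part of the SAP pick them up?**

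- Section 10.4 covers adverse events rated not related, and section 11.2 covers the rest. An event that is not an adverse event fits neither.
- Section 6.4.4 uses adverse events as shorthand for adverse events, incidents and expected side effects, but only for the missing-date rules. Section 10.4 sets its own abbreviations, and 11.2 does not adopt the shorthand.
- Section 13.1 lists no table for malfunctions, use errors or device deficiencies. It titles Table 14.3.1.2 as related treatment-emergent adverse events, while the mock tables in 13.2 number the two incident tables 14.3.1.3 and 14.3.1.4 and title the second as incidents.
- Listing 16.2.7.1 names adverse events, incidents and expected side effects, so it may show these events subject by subject.
- Section 12 declares only the change to symptom duration.

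**Step 3. Should the data exist?** Yes. Protocol 14.3 sends all incidents to the e-CRF, and replacement bottles are issued through its back-up randomisation module. The Primary Notification Form in Appendix B asks separately what went wrong with the device and what health effects followed, each if applicable, so it allows for an incident without health effects.

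**Step 4. Scale, for illustration only.** Let p be the assumed proportion of subjects with such an event and no adverse event, with n = 200 planned subjects (SAP section 4). The expected number omitted is n × p, and the chance that at least one is omitted is 1 − (1 − p)^n.

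| Assumed p | Expected omitted, 200 × p | Chance of at least one, 1 − (1 − p)^200 |
|---|---|---|
| 0.5% | 1 | 63% |
| 1% | 2 | 87% |
| 2% | 4 | 98% |
| 5% | 10 | >99.9% |

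Every value of p here is an assumption.

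**The case against.** The case for leaving the SAP alone has several parts.

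- *Nothing is lost to surveillance.* Protocol 14.4.1 has incidents notified within 24 or 48 hours, and 14.5.1 provides for manufacturer reports and trend reports. This stands, but it does not make the trial's own tables match their labels.
- *The events are still listed.* A reader might infer that a symptom-free malfunction appears in no table or listing at all. The documents do not support that, because Listing 16.2.7.1 names incidents. The gap concerns the 14.3.1.x tables and the 14.3.2.x listings.
- *Tolerance is the safety objective.* A reader might infer that incidents are the main safety output of the study. The documents do not say so: the stated objective is systemic and local tolerance, which related adverse events address, and Protocol 8.4 plans summaries by MedDRA class without promising a malfunction table. That limits the importance of the point. It does not remove the conflict, since 8.4 does ask for incidents to be summarised.
- *The planned malfunction check comes before exposure.* Priming takes place before the patient leaves the site, and first use is that evening. Such a failure therefore precedes any puff, and the incident tables use the Safety Set, defined by at least one puff. This is a fair limit on the priming example. The patient may still join the Safety Set with the replacement bottle, so a counting rule is needed. Failures during home use are not affected by this argument.
- *The protocol definition is not clean either.* It refers to a device made available on the market, and only Healsea Rescue is described as CE-marked, while Protocol 7.1.4 assesses incidents in both groups. This stands, and the fix has to address it.
- *The e-CRF may record malfunctions on the adverse event form with a relationship field*, in which case some would be counted in practice. That is possible, but the SAP does not say so.

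**Conclusion.** The point holds as a definitional conflict of minor weight. Applied as written, SAP 11.2 produces incident tables that are narrower than the protocol's definition of an incident, and the narrowing is not declared.

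The direction of the error follows from the wording; its size does not. The undercount is zero if no symptom-free malfunction, use error or information inadequacy occurs. A reader might turn an assumed rate into a count of missing incidents, but the documents give no rate. The range of 1 to 10 subjects rests on an assumed 0.5% to 5%, on all 200 subjects being counted in both arms, and on none of the events being accompanied by an adverse event.

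The primary analysis and the other efficacy results are untouched. The conclusion assumes that the SAP sentence is applied literally and that no e-CRF convention outside the two documents brings malfunctions into the adverse event data.

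**What to change.** 1. In SAP 11.2, replace the equation with related adverse events by the Protocol 14.2 definitions of incident and serious incident, and state that they apply to the devices of both arms.
2. In Table 14.3.1.1, report by arm, as separate rows, (a) device-related adverse events and (b) device malfunctions, use errors and information inadequacies, with or without an adverse event. A row for replacement bottles is optional.
3. State how failures found at the priming check, before first use, are counted, given that the tables use the Safety Set.
4. Align the titles and numbers of the 14.3.1.x tables between the list in 13.1 and the mock tables in 13.2.
5. Record the change in SAP section 12.

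The cost is SAP wording and one or two table rows, from data that Protocol 14.3 already requires in the e-CRF. The reported incident count may come out slightly higher. Keeping related adverse events in their own row preserves the tolerance result that the present wording would give.
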